# **PROTOCOL SUMMARY**

## Background

Lung cancers that harbor chromosomal rearrangements of anaplastic lymphoma kinase (ALK) constitute about 3-5% of non-small-cell lung cancers (NSCLCs) and are highly responsive to small-molecule tyrosine kinase inhibitors (TKIs) that target ALK. Standard treatment of patients with advanced ALK-positive NSCLC has recently shifted from sequential crizotinib followed by more potent second-generation ALK TKIs to front-line second-generation TKIs. Whereas most patients derive clinical benefit from second-generation ALK TKIs, acquired resistance invariably develops and leads to clinical relapse.

Lorlatinib is a third-generation, oral, reversible, adenosine triphosphate (ATP)-competitive, macrocyclic TKI of ALK and ROS1. Compared with second-generation inhibitors, lorlatinib was specifically designed to penetrate the central nervous system (CNS) and to overcome known secondary resistance mutations in the ALK tyrosine kinase domain. Preclinical studies demonstrate that lorlatinib is more potent than earlier-generation TKIs against nonmutant ALK and retains potency against most known single ALK resistance mutations, including the highly refractory ALK G1202R solvent front mutation.

In the pivotal single arm, multicenter Phase 2 study, treatment with lorlatinib showed clinically relevant response rates and durable response in patients with ALK-positive NSCLC who had previously received at least 1 ALK TKI, including the second-generation drugs ceritinib and alectinib. In the cohort of patients previously treated with a second-generation ALK TKI (number of patients [N]=28), objective responses were observed in 9 patients (32% [95% confidence interval [CI]: 15.9-52.4]). Substantial intracranial activity was also observed in these patients suffering from frequent brain metastases. The proportion of patients with objective intracranial response to lorlatinib was 55.6% (95% CI: 21.2-86.3) in patients with at least 1 measurable brain lesion at baseline (N=9). The overall and intracranial median duration of response (DoR) were not reached (95% CI: 4.1 months – not reached; duration of follow-up 7 months).

# Rationale

On the basis of pivotal Phase 1/2 Study B7461001, lorlatinib received conditional marketing authorization by the Indian Ministry of Health for the treatment of ALK fusion gene-positive unresectable advanced and/or recurrent NSCLC with resistance or intolerance to ALK TKI(s).

In view of the lack of Indian participants from Study B7461001 and of the limited number from the ongoing Phase 3 Study B7461006 (CROWN), the Indian Ministry of Health requested the Sponsor to conduct a post-approval study to obtain additional data on participants in India. The study will be conducted as a post-authorization safety study (PASS).

#### **Study Objectives and Endpoints**

#### Primary Objective

• To evaluate the safety and tolerability of single-agent lorlatinib in participants with unresectable advanced and/or recurrent ALK-positive NSCLC with resistance or intolerance to at least 1 prior ALK inhibitor treatment.

#### Secondary Objective

• To evaluate overall and intracranial antitumor activity of single-agent lorlatinib in participants with unresectable advanced and/or recurrent ALK-positive NSCLC with resistance or intolerance to at least 1 prior ALK inhibitor treatment.

#### Primary Endpoint

• Incidence of adverse events (AEs).

#### Secondary Endpoints

• Confirmed objective response rate (ORR), confirmed intracranial objective response rate (IC-ORR), DoR and intracranial duration of response (IC-DoR) as assessed by the Investigator using Response Evaluation Criteria in Solid Tumor (RECIST) version 1.1.

#### **Study Design**

This is a Phase 4, open-label, multicenter, non-randomized, prospective, single arm study to evaluate the safety and tolerability of lorlatinib in adult participants with unresectable advanced and/or recurrent ALK-positive NSCLC with resistance or intolerance to at least 1 prior ALK inhibitor treatment.

This study will enroll enough participants to ensure that 100 participants are treated with lorlatinib.

#### **Study Treatments**

Participants will take lorlatinib at the approved dose of 100 mg once daily (QD). Participants will be treated until disease progression, participant refusal/lost to follow-up, or unacceptable toxicity.

At the end of study, participants who are on treatment and benefiting from lorlatinib treatment will be moved to commercially available lorlatinib (if considered appropriate by the Investigator) as soon as feasible.

## Statistical Methods

The study's objectives are to evaluate the safety, tolerability and antitumor activity of single-agent lorlatinib. This study will enroll enough participants to ensure that 100 participants are treated with lorlatinib. With 100 participants, any AE rate can be estimated with the maximum standard error of 0.05. All participants who receive at least 1 dose of lorlatinib will be included in the safety and antitumor activity analyses, unless otherwise specified.

## Analysis of Primary Endpoint

AEs will be graded by the Investigator according to the CTCAE version 4.03 and coded using the Medical Dictionary for Regulatory Activities (MedDRA). The focus of AE summaries will be on treatment-emergent adverse events (TEAEs), those with an initial onset or increasing in severity after the first dose of study medication to at most 35 days post last dosing date or the date of initiation of a new anticancer therapy. The number and percentage of participants who experienced any AE, serious adverse event (SAE), treatment-related AE, and treatment-related SAE will be summarized.

#### Additional Safety Analyses

Other safety parameters, including study treatment exposure, laboratory, electrocardiogram (ECG), vital signs measurements, dose reductions due to AEs, and temporary and permanent discontinuations due to AEs, will be summarized descriptively.

#### Analysis of Secondary Endpoints

The following analyses of response will be performed according to the Investigator assessment using RECIST version 1.1.

## ORR

ORR is defined as the percent of participants with best overall response as confirmed complete response (CR) or confirmed partial response (PR) according to RECIST version 1.1. ORR will be provided along with the corresponding 95% CI based on Wilson's Score Method.

## IC-ORR

IC-ORR is defined as the percent of participants with intracranial response (ie, best overall intracranial response as confirmed CR or confirmed PR considering only intracranial lesions) relative to participants with CNS metastases at study entry. IC-ORR will be provided along with the corresponding 95% CI based on Wilson's Score Method.

# DoR

DoR is defined as the time from the first documentation of objective tumor response (confirmed CR or confirmed PR) to the first documentation of disease progression or death due to any cause, whichever occurs first. For participants whose responses proceed from PR to CR, the onset of PR is taken as the onset of response. DoR will be summarized in the population of participants with a confirmed CR or confirmed PR using the Kaplan Meier method and will be displayed graphically where appropriate. The median event time (if appropriate) and 2-sided 95% CI for the median will be provided. Censoring for DoR will be described in the statistical analysis plan (SAP). In case the number of participants with progressive disease (PD) after a confirmed CR or confirmed PR is small, the use of Kaplan Meier method may be limited and descriptive statistics may be provided.

# IC-DoR

*IC*-DoR is defined as the time from the first documentation of an intracranial objective response in the subgroup of participants with brain metastasis at baseline. Analyses similar to DoR will be repeated for IC-DoR considering participants with intracranial response (ie, best overall intracranial response as confirmed CR or confirmed PR considering only intracranial lesions).

# End of Study

The end of study is defined as 1 year after the "last participant first visit" (LPFV) date in the study.

# SCHEDULE OF ACTIVITIES

The Schedule of Activities table provides an overview of the protocol visits and procedures. Refer to STUDY PROCEDURES and ASSESSMENTS sections of the protocol for detailed information on each procedure and assessment required for compliance with the protocol.

The Investigator may schedule visits (unplanned visits) in addition to those listed on the Schedule of Activities, in order to conduct evaluations or assessments required to protect the wellbeing of the participant.

Visit Identifier	Screening	Cycle 1 (28 days)	Visit on Day 1 of Every Cycle	End of Treatment	Follow-Up 
Visit Window	≤28 days	Day 1	±2 days	$\pm 7$ days	
Informed consent 	X	2			
Tumor history	Х				
Medical history	Х				
Physical examination and vital signs	Х	Х	Х	Х	
Body weight		Х	Х	Х	
ECOG performance status	Х	Х	Х	Х	
Contraception check  (as appropriate)		Х	Х	X	Х
Laboratory					
Hematology	Х	(X)	Х	Х	
Blood chemistry	Х	(X)	Х	Х	
Lipids	Х	(X)	Х	Х	
Pregnancy test 	Х	Х	Х	Х	Х
Cardiac Monitoring					
12-Lead ECG 	Х	(X)	X (every cycle up to Cycle 5)	Х	
Treatment					
Lorlatinib			Orally once daily, conti	nuously	
Tumor Assessments					
CT or MRI imaging 	Х		X (every 12 weeks $\pm 1$ week)	Х	
Other Clinical Assessmen					
Serious and non-serious AEs 	Х	Х	Х	X	Х
Concomitant medications and non-drug supportive interventions 	Х	Х	Х	Х	Х

(X): No need to repeat if assessment performed within 7 days prior to Cycle 1 Day 1.

Abbreviations: AE=adverse event; CAP=chest abdomen pelvis; CRF=case report form; CT=computed tomography; CTCAE=Common Terminology Criteria for Adverse Events; ECG=electrocardiogram; ECOG=Eastern Cooperative Oncology Group; MRI=magnetic resonance imaging; NCI=National Cancer Institute; QTc=QT interval corrected for heart rate; RECIST=Response Evaluation Criteria in Solid Tumor; SAE=serious adverse event.

- 1. Informed consent must be obtained prior to undergoing any study-specific procedures that are not considered standard of care.
- 2. Contraceptive check: participant may be contacted by phone to confirm contraception is still appropriate per the protocol.

- 3. Pregnancy test: for female participants of childbearing potential, a serum or urine pregnancy test will be performed at Screening and at the Cycle 1 Day 1 visit. Results must be available before investigational product administration. Pregnancy tests will be also routinely repeated at every cycle during the active treatment period, at the end of treatment, at the short-term follow-up visit, and additionally whenever 1 menstrual cycle is missed or when potential pregnancy is otherwise suspected.
- 4. 12-lead ECGs: 3 consecutive 12-lead ECGs pre-dose will be performed approximately 2 minutes apart to determine mean PR interval and QTc interval at baseline (screening and Cycle 1 Day 1 if the ECG at screening is performed more than 7 days before Cycle 1 Day 1) and single ECGs will be performed at Day 1 of every cycle up to Cycle 5 and at the end of treatment. Additional ECGs may be collected as clinically indicated.
- 5. Tumor assessment: tumor assessments will include all known or suspected disease sites. CT or MRI scans of CAP and MRI of the brain will be performed at Screening and repeated every 12 weeks (±1 week). For all tumor assessments, the method of assessment that was used at Screening should be the same method used throughout the study. Responses will be confirmed ≥4 weeks after first occurrence of response, according to RECIST version 1.1 criteria. Tumor assessment should be repeated at the end of treatment if more than 6 weeks have passed since the last evaluation.
- 6. AE assessments: AEs should be documented and recorded into the electronic CRF at each visit using NCI CTCAE version 4.03. For AEs and SAEs, the active collection period to Pfizer or its designated representative begins from the time that the participant provides informed consent, through and including at least 28 calendar days and no more than 35 days after the last administration of the investigational product. If a participant begins a new anticancer therapy, the reporting period for non-serious AEs ends at the time the new treatment is started. SAEs and Death must be reported if it occurs during the SAE reporting period after the last dose of investigational product, irrespective of any intervening treatment.
- 7. Concomitant medications and non-drug supportive interventions: all concomitant medications and non-drug supportive interventions should be recorded in the CRF from 28 days prior to start of study treatment and up to at least 28 days and no more than 35 days after the last dose of study treatment.
- 8. Follow-up: at least 28 days, and no more than 35 days after discontinuation of treatment, participants will return to undergo contraception check, pregnancy test, review of concomitant medications, AE assessments, and review for resolution of any treatment-related toxicity.

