## 2. STUDY OBJECTIVES AND ENDPOINTS

	Objective	Estimands		Endpoints
Pr	imary			
•	To evaluate the safety and tolerability of single-agent lorlatinib in participants with unresectable advanced and/or recurrent ALK-positive NSCLC with resistance or intolerance to at least 1 prior ALK inhibitor treatment.	• The primary estimand is the incidence of AEs from the time of first dose to at most 35 days post last dosing date or the date of initiation of a new anticancer therapy for all participants who receive at least 1 dose of lorlatinib, regardless of dosing interruptions or dosing compliance.	•	Incidence of AEs.
Se	condary			
•	To evaluate overall and intracranial antitumor activity of single-agent lorlatinib in participants with unresectable advanced and/or recurrent ALK-positive NSCLC with resistance or intolerance to at least 1 prior ALK inhibitor treatment.	• The secondary estimand is the treatment effect of lorlatinib as assessed by the investigator from time of first dose (ORR and IC-ORR) or time of first response (DoR and IC-DoR) until progression is met, death or subsequent anticancer therapy is administered for all participants who receive at least 1 dose of lorlatinib without regard to tolerability or discontinuation from treatment.	•	Confirmed ORR, confirmed IC-ORR, DoR and IC-DoR as assessed by the Investigator using RECIST version 1.1.

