## 8.2. Reporting Period

For AEs and SAEs, the active reporting period to Pfizer or its designated representative begins from the time that the participant provides informed consent, which is obtained prior to the participant's participation in the study, ie, prior to undergoing any study-related procedure and/or receiving investigational product, through and including at least 28 calendar days and no more than 35 days after the last administration of the investigational product. SAEs occurring to a participant after the active reporting period has ended should be reported to the Sponsor if the Investigator becomes aware of them; at a minimum, all SAEs that the Investigator believes have at least a reasonable possibility of being related to study drug are to be reported to the Sponsor.

If a participant begins a new anticancer therapy, the AE reporting period for nonserious AEs ends at the time the new treatment is started. Death must be reported if it occurs during the SAE reporting period after the last dose of investigational product, irrespective of any intervening treatment.

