### 9.2. Sample Size Determination

This study will enroll enough participants to ensure that 100 participants are treated with lorlatinib. With 100 participants, any AE rate can be estimated with the maximum standard error of 0.05. All participants who receive at least 1 dose of lorlatinib in this study will be included in the safety and antitumor activity analyses unless otherwise specified.

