6. ANALYSES AND SUMMARIES

6.1. Primary Endpoint

6.1.1. Adverse Events

6.1.1.1. Main Analysis

Analysis set: Safety: All enrolled participants who take at least 1 dose of Lorlatinib **Analysis methodology**:

- AE incidence rate is the number of patients with any AE occurring at least once in the study population.
- All Adverse Events (AEs) will be coded using the MedDRA.
- All analyses will be based on treatment emergent events unless otherwise specified. Treatment emergent is defined in Section 3.5.1.

Intercurrent events and missing data:

• All data after the intercurrent event "start of subsequent anticancer therapy (-1 day)" or "35 days after treatment discontinuation" will be excluded from summaries but will be listed regardless of dosing interruptions or dosing compliance.

Summaries used for reporting:

- High-level summaries of adverse events (both All Causality and Treatment Related) will include the number and percent of participants with:
 - o Any Adverse Event;
 - o Serious AE;
 - o Adverse Events with CTCAE Grade 3-4;
 - o Grade 5 events;
 - o AEs associated with dose interruptions;
 - o AEs associated with dose reductions;
 - o AEs associated with withdrawal;

Additionally, the number of events reported for each of the categories above will be provided. Each unique adverse event at the PT level for a participant is included in the count. Seriousness, relatedness, toxicity grade, action taken (interruption, reduction, and withdraw) are as reported by the investigator on the adverse event CRF.

- Summaries by System Organ Class (SOC) and PT in decreasing frequency will be provided for:
 - o Treatment Emergent Events by Maximum Toxicity Grade (All Causality);
 - Treatment Emergent Events by Maximum Toxicity Grade (Treatment Related);

- Serious Treatment Emergent by Maximum Toxicity Grade Events (All Causality);
- Serious Treatment Emergent by Maximum Toxicity Grade Events (Treatment Related);

An event will be considered treatment related if the investigator considered the event related to the study drugs or this information is unknown.

Clustered adverse events will be summarized by maximum CTCAE grade and
causality (all-causality and treatment-related) together with other adverse events.
Adverse Events pertaining to each cluster will be summarized separately, by cluster.
The clustered events are described in a list in the product's Safety Review Plan
maintained by the Sponsor.

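### SAEs that begin after a new anticancer therapy are collected but only listed; a supplementary SAE summary to 35 days after the last dose would show them

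*Protocol*

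**What the plan says.** **Collection.** Footnote 6 of the Schedule of Activities collects AEs and SAEs from consent "through and including at least 28 calendar days and no more than 35 days after the last administration of the investigational product". It then separates the two kinds of event. For non-serious events: "If a participant begins a new anticancer therapy, the reporting period for non-serious AEs ends at the time the new treatment is started". For SAEs and deaths, the event "must be reported if it occurs during the SAE reporting period after the last dose of investigational product, irrespective of any intervening treatment". Protocol 8.2 also stops only non-serious AEs at the new therapy, but its second sentence names death alone: "Death must be reported if it occurs during the SAE reporting period after the last dose of investigational product, irrespective of any intervening treatment". The same section asks for SAEs that come to light after the active period, and at the least those thought possibly related to study drug.

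**Analysis.** The primary estimand in Protocol 2 and 9.1.1 runs from first dose to at most 35 days after the last dose "or the date of initiation of a new anticancer therapy for all participants who receive at least 1 dose of lorlatinib". Protocol 9.6 uses the same window for treatment-emergent AEs. SAP 2.1.1 ends it on the day before the new therapy and names that therapy as an intercurrent event. SAP 3.5.1 defines the on-treatment period in the same spirit, and SAP 3.5 has safety data from outside that period listed only. SAP 6.1.1.1 says that data after the new therapy "will be excluded from summaries but will be listed regardless of dosing interruptions or dosing compliance". None of these places makes an exception for serious or related events.

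**Deaths.** SAP 6.1.1.1 separately tabulates participants who died, and who died within 28 days of the last dose, from the Notice of Death. It states no cut at new therapy for that table.

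**The concern.** The protocol takes the trouble to collect SAEs past a change of therapy, and Investigator causality is recorded for each (Protocol 8.9). The SAP then keeps those events out of the summaries.

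Suppose the last lorlatinib dose is on day 0, the next drug starts on day 5, and on day 10 there is an SAE that the Investigator attributes to lorlatinib. The event is reported and judged related, yet it is missing from the SAE tables, the treatment-related SAE tables and the basic-results SAE table of SAP 6.1.1.2. If it is fatal, it is also missing from the Grade 5 rows.

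This is a post-authorization safety study requested by a regulator, and safety is its only primary objective. A reader of the headline related-SAE percentage will not see that some SAEs attributed to lorlatinib sit only in a listing. Relative to what was collected, the difference can run only one way.

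**Working it through.** **1. The plan's own figure.** Protocol 9.2 states: "With 100 participants, any AE rate can be estimated with the maximum standard error of 0.05". With n = 100 and p = 0.5, SE = sqrt(0.5 × 0.5 / 100) = 0.05. This reproduces and is not in dispute. For scale, at an illustrative rate of 5% the SE is sqrt(0.05 × 0.95 / 100) = 0.022.

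**2. Collection against tabulation after a new therapy.**

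| Event with onset after the switch, within 35 days of last dose | Collected? | In AE summaries? |
|---|---|---|
| Non-serious AE | No | No |
| SAE, not related | Yes (footnote 6) | No, listed only |
| SAE, related or causality unknown | Yes (footnote 6) | No, listed only |
| Fatal SAE | Yes (footnote 6, Protocol 8.2) | Not in the Grade 5 AE rows; the death itself is in the deaths table |

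SAP 6.1.1.1 counts an event as treatment related if the Investigator says so or if causality is unknown. That rule classifies events already inside the window and brings none back from outside it.

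**3. Length of the gap.** If new therapy starts s days after the last dose, up to 35 − s days of SAE collection feed listings only: 28, 21 or 14 days for s = 7, 14 or 21. Where collection closes at day 28, the gap is 28 − s: 21, 14 or 7 days.

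**4. Possible size (illustration only).** The documents give no switching rate, time to switch or SAE rate. All four inputs below are assumptions:

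- f, share of treated participants starting a new therapy within 35 days of the last dose: 10% to 50%
- s, day of that start: 7 to 21
- r, SAE risk per 35 days: 5% to 20%
- q, share of those affected who have no earlier counted SAE: 0.7 to 1.0

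The factor q is needed because a participant who already has a counted SAE does not change the participant-level total.

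Expected participants added per 100 = 100 × f × [1 − (1 − r)^((35 − s)/35)] × q.

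- Low: 100 × 0.10 × [1 − 0.95^0.4] × 0.7 = 100 × 0.10 × 0.0203 × 0.7 = 0.14
- Mid, q = 0.7: 100 × 0.30 × [1 − 0.90^0.6] × 0.7 = 100 × 0.30 × 0.0613 × 0.7 = 1.29
- Mid, q = 1.0: 100 × 0.30 × 0.0613 = 1.84
- High: 100 × 0.50 × [1 − 0.80^0.8] × 1.0 = 100 × 0.50 × 0.1635 = 8.17

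The chance that at least one of 100 participants is affected is 1 − (1 − f × risk × q)^100, where risk is the bracketed term. In the mid case it is 0.73 (q = 0.7) to 0.84 (q = 1.0). The part judged related to lorlatinib cannot be sized from anything in the documents.

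**The case against.** The strongest reply is that nothing here is an error. The cut at new therapy appears consistently in both documents, and the SAP names it as an intercurrent event with stated handling. Footnote 6 and Protocol 8.2 govern reporting to the sponsor, and a reporting period may properly be wider than an analysis window. The related-SAE count in Protocol 9.6 directly follows the sentence that defines the treatment-emergent window, so the protocol does not promise a count to day 35 regardless of a switch. All of this stands. A reader might infer that the primary AE rates are biased, or that the estimand must be rewritten; the documents do not support either. Folding post-switch events into a single-arm lorlatinib count would add events caused by the next drug, and the rule that treats unknown causality as related would push the count up further.

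A reader might also infer that fatal events vanish from the summaries. They do not: the deaths table covers them, although the Grade 5 AE rows remain affected.

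Nor do the documents show that much of the cohort switches quickly. Two features limit the effect. Toxicity that began on lorlatinib and persists after the switch is still counted, because SAP 3.5.1 works on first occurrence or worsening. Protocol 8.6 also keeps progression, and hospitalization for it, out of SAE reporting unless fatal.

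None of this answers the narrower point. Non-fatal SAEs attributed to lorlatinib after a switch are collected and tabulated nowhere, and neither document says why.

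**Conclusion.** The gap between collection and tabulation is real and can be read directly from the two documents. It is a consequence of a deliberate estimand, so it calls for an added summary and not a correction of the primary analysis. The size is unknown: about 0.1 to 8 participants per 100 under the assumed ranges and about 1 to 2 in the mid case, all conditional on assumed switching and SAE rates. The mid case is well below the stated maximum SE of 5 percentage points, but is of the same order as the SE of about 2 points for a rate near 5%. Individual SAE terms may rest on a few participants, so even one omission could show. This is a cheap improvement to the safety report.

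**What to change.** Keep the primary estimand. Add to SAP 6.1.1.1 a supplementary summary of all SAEs, treatment-related SAEs and Grade 5 events with onset up to 35 days after the last dose, regardless of new anticancer therapy. Use two rows: onset before the start of new therapy, and onset on or after it. In the second row, show SAEs the Investigator judged related apart from those of unknown causality. A footnote should say that Protocol 8.6 records fatal progression as a Grade 5 SAE, so that row will include deaths from the malignancy.

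Two wording points should be settled with it:

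- Align Protocol 8.2, which names only death as reportable irrespective of later treatment, with footnote 6, which names SAEs and death.
- Reconcile the two definitions of new anticancer therapy. SAP 3.5.1 counts follow-up radiation to any target or non-target lesion, while SAP 5.2.3 counts only radiation of curative intent. SAP 5.2.3 also looks for the earliest date after the first lorlatinib dose, so a qualifying procedure during dosing could end the on-treatment period while the participant is still taking the drug.

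The cost is one extra table from data already collected. Because the primary endpoint and its analysis do not change, the table should not trigger the amendment that Protocol 9 and SAP 2 require for major modifications; the Protocol 8.2 wording is a separate protocol edit. The downside is that some post-switch SAEs will be due to the next therapy, which the two rows make visible.
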